### 5.5.3 Other Endpoints

All other endpoints in Section 2.4.1 will be described descriptively in appropriate summary tables.

### 5.5.4 Safety Endpoints

Safety endpoints will be described by summary tables on the Safety Analysis Set (SAS).

Treatment-emergent AEs, treatment-emergent drug-related AEs, treatment-emergent serious AEs (SAE), treatment-emergent drug-related SAEs, treatment-emergent AEs leading to drug withdrawal and treatment-emergent drug-related SAEs leading to drug withdrawal will be presented in summary tables of the number and percentage of patients with at least one event, and the number of events, by primary SOC and by PT within SOC. For treatment-emergent AEs and treatment-emergent drug-related AEs, these summaries will also be provided by maximum severity. Maximum severity is defined by the most severe AE per patient, SOC and PT. An overview will summarize incidences in all listed AE categories including deaths.

Vital signs will be summarized by visit including changes from baseline, as well as a shift table with categories: normal, abnormal/non-clinically significant, and abnormal/clinically significant. For physical examination, frequency counts of the complete examination (including all body systems and the vulvar region) at Screening 1 and Week 12 (or EoT) visits as well as the results of the abbreviated physical examination at the baseline and FU visits (if judged necessary by the investigator), will be reported in both

a table with percentages as well as a shift table with categories: normal, abnormal/non-clinically significant, and abnormal/clinically significant. Frequency counts and percentage of urine pregnancy tests will also be presented.

### 5.5.5 Overview of Analyses

Analyses of other and safety endpoints are descriptive and exploratory. Planned analyses of primary, secondary and other endpoints for efficacy, including patient related outcomes, are summarized in the following table.

Table 5 Overview of primary and sensitivity analyses of endpoints for efficacy (with strategy, analysis set and imputation)

Sequence	Endpoint	Primary Analysis	Sensitivity Analyses
Primary	Change in weekly mean WI-NRS from patient's diary from Baseline to W12 from patient's diary	treatment policy, FAS, MI	1: treatment policy, FAS, 2: treatment policy, MFAS 3: treatment policy, PPS 4. while on treatment, FAS
Secondary	Change in weekly mean WP-NRS from patient's diary from Baseline to W12	treatment policy, FAS, MI	1: treatment policy, FAS, 2: treatment policy, MFAS 3: treatment policy, PPS 4. while on treatment, FAS
	Change in Skindex-29 domains from Baseline to W12	treatment policy, FAS, MI	1: treatment policy, FAS, 2: treatment policy, MFAS 3: treatment policy, PPS 4. while on treatment, FAS
	A $\geq 4$ -point improvement in weekly mean WI-NRS from patient's diary	treatment policy, FAS, worst case imputation	
	A $\geq 4$ -point improvement in weekly mean WP-NRS from patient's diary	treatment policy, FAS, worst case imputation	
	A $\geq 3$ -point improvement in weekly mean WI-NRS from patient's diary	treatment policy, FAS, worst case imputation	
	A $\geq 3$ -point improvement in weekly mean WP-NRS from patient's diary	treatment policy, FAS, worst case imputation	

W = Week. Worse case imputation = missing endpoint data is assumed to be no response

### 5.6 Changes and Clarifications to Analyses Planned in the Study Protocol

There are two changes to the sub-group analyses specified in section 9.4.6 in the protocol:

- The stratification by country will not be carried out as the study is carried in only one country
- Similarly, the stratification by site is deemed superfluous due to both the smaller sample size than expected, and possibly sites with very small sample sizes

In section 9.4.8 the exploratory endpoint burden living with VLS is only assessed at Screening and will only be listed, not described in summary tables.

Statistical within-treatment group pre-post testing was added to descriptive summary tables of selected endpoint as specified above.

## 5.7 Implementation

The SAP will be implemented by means of statistical programming specifications with technical details of implementation and the level of validation of programming. Derived datasets will be produced following raw-to-derived data specifications, tables, figures and listings (TFL) according to approved TFL shell versions.

## 7 Deliverables

Based on a TFL shells document, the following tables, figures and listings will be produced.

### 7.1 In-text Tables

In-text tables will be produced identical to selected post-text tables by content and in the layout of the report.

## 7.2 In-text Figures

In-text figures will be copied from selected post-text figures.

## 7.3 Post-text Tables

The following post-text tables will be produced. All tables will summarize results by treatment group.

Table 6 Table of Content of Post-Text Tables

14.1	Disposition, Baseline Characteristics, Exposure and Concomitant Therapies
Table 14.1.1	Patient Disposition - Summary (Screened Set)
Table 14.1.2	Analysis Sets - Summary (Full Analysis Set)
Table 14.1.3.1	Inclusion and Exclusion Criteria - Summary (Full Analysis Set)
Table 14.1.3.2	Protocol Deviations - Summary (Full Analysis Set)
Table 14.1.3.3	Major Protocol Deviations - Summary (Full Analysis Set)
Table 14.1.4.1	Demographics - Summary (Full Analysis Set)
Table 14.1.4.2	Demographics - Summary (Modified Full Analysis Set)
Table 14.1.4.3	Demographics - Summary (Safety Analysis Set)
Table 14.1.4.4	Demographics - Summary (Per-Protocol Set)
Table 14.1.5.1	Baseline Disease Characteristics - Summary (Full Analysis Set)
Table 14.1.5.2	Baseline Disease Characteristics - Summary (Modified Full Analysis Set)
Table 14.1.5.3	Baseline Disease Characteristics - Summary (Safety Analysis Set)
Table 14.1.5.4	Baseline Disease Characteristics - Summary (Per-Protocol Set)
Table 14.1.6	Vital Signs, Height, and Weight at Baseline - Summary (Full Analysis Set)
Table 14.1.7.1	Medical and Surgical History - Summary by SOC and PT (Full Analysis Set)
Table 14.1.7.2	Concurrent Diagnoses at Screening - Summary by SOC and PT (Full Analysis Set)
Table 14.1.8.1	Prior Drug and Non-Drug Therapies - Summary by ATC Class and PT (Full Analysis Set)
Table 14.1.8.2	Prior Ongoing Drug and Non-Drug Therapies - Summary by ATC Class and PT (Full Analysis Set)
Table 14.1.8.3	Concomitant Drug and Non-Drug Therapies - Summary by ATC Class and PT (Full Analysis Set)
Table 14.1.9	Exposure and Treatment Compliance - Summary (Full Analysis Set)
14.2	Efficacy Data
14.2.1	Primary Efficacy Endpoint
Table 14.2.1.1	Weekly mean WI-NRS from patient's diary - Summary by Visit, Observed Cases (Full Analysis Set)
Table 14.2.1.2	Weekly mean WI-NRS from patient's diary - Summary by Visit, Averaged Multiple Imputations, Treatment policy Strategy (Full Analysis Set)
Table 14.2.1.3	Weekly mean WI-NRS from patient's diary - Summary by Visit, Observed Cases (Modified Full Analysis Set)
Table 14.2.1.4	Weekly mean WI-NRS from patient's diary - Summary by Visit, Observed Cases (Per-Protocol Set)
Table 14.2.1.5	Weekly mean WI-NRS from patient's diary - Summary by Visit, Observed Cases, While on treatment Strategy (Full Analysis Set)
Table 14.2.1.6	Change in weekly mean WI-NRS from patient's diary at Week 12 - Primary Analysis using MI, Treatment policy Strategy (Full Analysis Set)
Table 14.2.1.7	Change in weekly mean WI-NRS from patient's diary at Week 12 - Sensitivity Analysis, Treatment policy Strategy (Full Analysis Set)
Table 14.2.1.8	Change in weekly mean WI-NRS from patient's diary at Week 12 - Sensitivity Analysis, Treatment policy Strategy (Modified Full Analysis Set)

Table 14.2.1.9	Change in weekly mean WI-NRS from patient's diary at Week 12 - Sensitivity Analysis, Treatment policy Strategy (Per-Protocol Set)
Table 14.2.1.10	Change in weekly mean WI-NRS from patient's diary at Week 12 - Sensitivity Analysis, While on treatment Strategy (Full Analysis Set)
14.2.2	Secondary Efficacy Endpoints
Table 14.2.2.1	Weekly mean WP-NRS from patient's diary - Summary by Visit, Observed Cases (Full Analysis Set)
Table 14.2.2.2	Weekly mean WP-NRS from patient's diary - Summary by Visit, Averaged Multiple Imputations, Treatment policy Strategy (Full Analysis Set)
Table 14.2.2.3	Weekly mean WP-NRS from patient's diary - Summary by Visit, Observed Cases (Modified Full Analysis Set)
Table 14.2.2.4	Weekly mean WP-NRS from patient's diary - Summary by Visit, Observed Cases (Per-Protocol Set)
Table 14.2.2.5	Weekly mean WP-NRS from patient's diary - Summary by Visit, Observed Cases, While on treatment Strategy (Full Analysis Set)
Table 14.2.2.6	Change in weekly mean WP-NRS from patient's diary at Week 12 - Primary Analysis using MI, Treatment policy Strategy (Full Analysis Set)
Table 14.2.2.7	Change in weekly mean WP-NRS from patient's diary at Week 12 - Sensitivity Analysis, Treatment policy Strategy (Full Analysis Set)
Table 14.2.2.8	Change in weekly mean WP-NRS from patient's diary at Week 12 - Sensitivity Analysis, Treatment policy Strategy (Modified Full Analysis Set)
Table 14.2.2.9	Change in weekly mean WP-NRS from patient's diary at Week 12 - Sensitivity Analysis, Treatment policy Strategy (Per-Protocol Set)
Table 14.2.2.10	Change in weekly mean WP-NRS from patient's diary at Week 12 - Sensitivity Analysis, While on treatment Strategy (Full Analysis Set)
Table 14.2.2.11	Skindex-29 domains - Summary by Visit, Observed Cases (Full Analysis Set)
Table 14.2.2.12	Skindex-29 domains - Summary by Visit, Averaged Multiple Imputations, Treatment policy Strategy (Full Analysis Set)
Table 14.2.2.13	Skindex-29 domains - Summary by Visit, Observed Cases (Modified Full Analysis Set)
Table 14.2.2.14	Skindex-29 domains - Summary by Visit, Observed Cases (Per-Protocol Set)
Table 14.2.2.15	Skindex-29 domains - Summary by Visit, Observed Cases, While on treatment Strategy (Full Analysis Set)
Table 14.2.2.16	Change in Skindex-29 domains at Week 12 - Primary Analysis using MI, Treatment policy Strategy (Full Analysis Set)
Table 14.2.2.17	Change in Skindex-29 domains at Week 12 - Sensitivity Analysis, Treatment policy Strategy (Full Analysis Set)
Table 14.2.2.18	Change in Skindex-29 domains at Week 12 - Sensitivity Analysis, Treatment policy Strategy (Modified Full Analysis Set)
Table 14.2.2.19	Change in Skindex-29 domains at Week 12 - Sensitivity Analysis, Treatment policy Strategy (Per-Protocol Set)
Table 14.2.2.20	Change in Skindex-29 domains at Week 12 - Sensitivity Analysis, While on treatment Strategy (Full Analysis Set)
Table 14.2.2.21	A $\geq$ 4-point improvement in weekly mean WI-NRS from patient's diary at Week 12 - Analysis using Worst Case Imputation, Treatment policy Strategy (Full Analysis Set)
Table 14.2.2.22	A $\geq$ 4-point improvement in weekly mean WI-NRS from patient's diary at Week 12 - Analysis using Observed Cases, Treatment policy Strategy (Full Analysis Set)
Table 14.2.2.23	A $\geq$ 4-point improvement in weekly mean WP-NRS from patient's diary at Week 12 - Analysis using Worst Case Imputation, Treatment policy Strategy (Full Analysis Set)
Table 14.2.2.24	A $\geq$ 4-point improvement in weekly mean WP-NRS from patient's diary at Week 12 - Analysis using Observed Cases, Treatment policy Strategy (Full Analysis Set)
Table 14.2.2.25	A $\geq$ 3-point improvement in weekly mean WI-NRS from patient's diary at Week 12 - Analysis using Worst Case Imputation, Treatment policy Strategy (Full Analysis Set)

Table 14.2.2.26	A $\geq$ 3-point improvement in weekly mean WI-NRS from patient's diary at Week 12 - Analysis using Observed Cases, Treatment policy Strategy (Full Analysis Set)
Table 14.2.2.27	A $\geq$ 3-point improvement in weekly mean WP-NRS from patient's diary at Week 12 - Analysis using Worst Case Imputation, Treatment policy Strategy (Full Analysis Set)
Table 14.2.2.28	A $\geq$ 3-point improvement in weekly mean WP-NRS from patient's diary at Week 12 - Analysis using Observed Cases, Treatment policy Strategy (Full Analysis Set)
14.2.3	Other Efficacy Endpoints and Patient Reported Outcomes
Table 14.2.3.1	A complete response (score<1) in weekly mean WI-NRS recorded in the patient's diary – Summary by Visit (Full Analysis Set)
Table 14.2.3.2	A complete response (score<1) in weekly mean WI-NRS recorded in the patient's diary – Summary by Visit (Full Analysis Set)
Table 14.2.3.3	WI-NRS from in-clinic visits - Summary by Visit (Full Analysis Set)
Table 14.2.3.4	WP-NRS from in-clinic visits - Summary by Visit (Full Analysis Set)
Table 14.2.3.5	WPP-NRS from in-clinic visits - Summary by Visit (Full Analysis Set)
Table 14.2.3.6	Improvement and Important Improvement in PGIC for WI, WP, and WPP - Summary by Visit (Full Analysis Set)
Table 14.2.3.7	ICIQ-UI-SF - Summary by Visit (Full Analysis Set)
Table 14.2.3.8	Menopausal status and Menstrual cycle status - Summary by Visit (Full Analysis Set)
Table 14.2.3.9	VQLI total score - Summary by Visit (Full Analysis Set)
Table 14.2.3.10	VASSI Total, Area, and Sign Scores - Summary by Visit (Full Analysis Set)
Table 14.2.3.11	Clinician's Global Assessment (CGA) of VLS - Summary by Visit (Full Analysis Set)
Table 14.2.3.12	Improvement in CGIC - Summary by Visit (Full Analysis Set)

14.3	Safety Data
14.3.1	Adverse Events
Table 14.3.1.1	Adverse Events - Overview (Safety Analysis Set)
Table 14.3.1.2	Treatment-emergent Adverse Events - Summary by SOC and PT (Safety Analysis Set)
Table 14.3.1.3	Treatment-emergent Adverse Events - Summary by Maximum Severity, SOC and PT (Safety Analysis Set)
Table 14.3.1.4	Treatment-emergent Drug-related Adverse Events - Summary by SOC and PT (Safety Analysis Set)
Table 14.3.1.5	Treatment-emergent Drug-related Adverse Events - Summary by Maximum Severity, SOC and PT (Safety Analysis Set)
Table 14.3.1.6	Treatment-emergent Serious Adverse Events - Summary by SOC and PT (Safety Analysis Set)
Table 14.3.1.7	Treatment-emergent Drug-related Serious Adverse Events - Summary by SOC and PT (Safety Analysis Set)
Table 14.3.1.8	Treatment-emergent Adverse Events Leading to Drug Withdrawal - Summary by SOC and PT (Safety Analysis Set)
14.3.2	Laboratory Parameters
Table 14.3.2.1	Urine Pregnancy Tests - Summary by Visit (Safety Analysis Set)
14.3.3	Vital Signs
Table 14.3.3.1	Vital Signs - Summary by Visit (Safety Analysis Set)
Table 14.3.3.2	Vital Signs - Shift Table by Visit (Safety Analysis Set)
14.3.4	Physical Examination
Table 14.3.4.1	Physical Examination - Summary by Visit (Safety Analysis Set)
Table 14.3.4.2	Physical Examination - Shift Table by Visit (Safety Analysis Set)

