9.2 Sample size determination

Sixty two (62) patients will be screened. 33 patients will be randomised in a 1:1 ratio of MC2-25 cream to MC2-25 vehicle. For a two-sided test with a 5% level of significance and an effect size of 1 standard deviation, this sample size will provide adequate power ($\geq 78\%$) to compare mean change in mean weekly WI-NRS from Baseline to Week 12 between MC2-25 cream and MC2-25 vehicle with 16 to 17 patients per treatment group.

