### 3.2.2 Summarizing Continuous Data

Continuous data including scores will be summarized by arithmetic mean, standard deviation (SD), median, quartiles, and ranges. Quartiles are given as (*lower quartile, upper quartile*) and ranges as (*minimum, maximum*). The number of non-missing values will also be displayed. Per post-baseline visit, summaries of changes from baseline in primary and secondary endpoints, on WI-NRS and WP-NRS, will also include p-values of t-tests on the change within each treatment group.

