### Multiple Imputation Procedure

Applicable to all primary and secondary endpoints with MI, the procedural steps are as follows. On 20 multiple complete imputed datasets as produced according to the instructions in Section 4.7.2, each dataset will be analyzed the same way. After pooling the estimates and standard errors, results will be aggregated following Rubin's rule to yield one estimate and associated standard error, and to calculate the 95% confidence interval for the treatment difference or odds ratio between treatments, respectively [11]. In data listings, multiply imputed values are described by mean values.

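### Within-arm t-tests on averaged multiple imputations (SAP Tables 14.2.1.2 and 14.2.2.2) would be anti-conservative; define 'averaged' and keep these tests off those tables

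*SAP*

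**What the plan says.** SAP Table 6 (section 7.3) lists three by-visit summaries on averaged imputations in the full analysis set: Table 14.2.1.2 for weekly mean WI-NRS, Table 14.2.2.2 for weekly mean WP-NRS and Table 14.2.2.12 for the Skindex-29 domains. Each title contains "Summary by Visit, Averaged Multiple Imputations, Treatment policy Strategy (Full Analysis Set".

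Section 3.2.2 sets their content: "Continuous data including scores will be summarized by arithmetic mean, standard deviation (SD), median, quartiles, and ranges". For changes from baseline in WI-NRS and WP-NRS, the post-baseline summaries "will also include p-values of t-tests on the change within each treatment group". Section 5.6 confirms that within-arm pre-post testing was added to the descriptive tables. Nothing exempts the averaged-imputation tables.

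The SAP does not define 'averaged' for tables. The nearest statement is in section 5.5, on listings: "In data listings, multiply imputed values are described by mean values". That section describes Rubin's rule for the treatment difference and the odds ratio between arms; it does not mention within-arm summaries or tests.

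Section 4.7.2 specifies 20 imputations, made separately in each arm and visit by visit. The predictors are menopausal status, ICIQ-UI-SF score, the baseline value and the earlier visits, so the Week 12 model has six.

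**The concern.** A mean of 20 draws is close to the regression prediction for that patient. An ordinary t-test on data completed in this way divides by the full arm size and counts each filled-in value as an independent observation. The filled-in values in fact all come from a model fitted to the patients who were observed, so they carry little new information. The uncertainty of the imputation is left out and the p-value tends to be too small.

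The tables concern the primary endpoint and one secondary endpoint. SAP section 7.1 builds in-text tables from selected post-text tables, so these p-values could reach the body of the report. They would stand beside an observed-case summary and a Rubin-pooled analysis that treat uncertainty differently, with no explanation of the difference.

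**Working it through.** **Inputs from the documents**
- Arm size: "33 patients will be randomised in a 1:1 ratio of MC2-25 cream to MC2-25 vehicle", "with 16 to 17 patients per treatment group" (protocol 9.2).
- Two-sided 5% level (protocol 9.2; SAP 5.1).
- 20 imputations and the imputation model (SAP 4.7.2).

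**Assumed, because the documents give no figure**
- 1 to 5 patients per arm missing at Week 12, dropping out completely at random.
- Normal data with between-visit correlation 0.3, 0.5 or 0.7. The standard deviation (SD) cancels in the ratios.

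**Step 1: the plan's own figure.** Protocol 9.2 states at least 78% power for an effect of 1 SD. With a two-sample t-test, the noncentrality is 1/√(1/16 + 1/17) = 2.871 on 31 degrees of freedom, which gives 79.4%. With 16 per arm the power is 78.1%. The stated figure is reproduced. It concerns the between-arm comparison; the documents give no operating figure for the averaged-imputation tables.

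**Step 2: hand check of the mechanism.** Suppose the SD is right but the imputed means add no information. The true standard error is then SD/√(n − k) with k missing, while the test uses SD/√n. Its effective critical value is t(0.975; n − 1) × √((n − k)/n). For n = 17, t = 2.120:

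| k missing | effective critical value | actual two-sided level |
|---|---|---|
| 0 | 2.120 | 5.0% |
| 1 | 2.120 × √(16/17) = 2.057 | 5.6% |
| 2 | 2.120 × √(15/17) = 1.991 | 6.4% |
| 3 | 2.120 × √(14/17) = 1.924 | 7.2% |
| 5 | 2.120 × √(12/17) = 1.781 | 9.4% |

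**Step 3: simulation under no mean change.** One arm of 16 or 17, baseline plus four visits, monotone dropout, Bayesian regression imputation with the SAP's predictors and 20 draws, 3,000 to 4,000 runs per setting. Monte Carlo error is about 0.4 to 0.5 percentage points. Actual level of the nominal 5% within-arm t-test:

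| missing per arm | each patient's draws averaged |
|---|---|
| 1 | about 5-6% |
| 2 | about 6-7% |
| 3 | about 7-10% |
| 4 | about 9-10% |
| 5 | about 10-12% |

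Over the same range, the observed-case t-test stays at 4-6% and Rubin pooling gives 1-4%, which is conservative. With 1 to 4 missing and correlation 0.5, averaging the 20 summary statistics instead of the patient values gives about 4-5%.

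**Step 4: is the SD too small?** In large samples the ratio of averaged to complete-data SD is √[(1 − f) + f(R² + (1 − R²)/20)], where f is the fraction missing and R² the share of variance that the imputation model explains. With f = 0.18 and R² = 0.5, it is √(0.82 + 0.18 × 0.525) = 0.956, a shortfall of about 4%. At this trial's size, noise in the six-predictor model offsets most of that. Simulated ratios to the complete-data SD, n = 17, correlation 0.5:

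| missing | averaged SD | pooled within-imputation SD | averaged ÷ pooled |
|---|---|---|---|
| 1 | 0.993 | 1.037 | 0.958 |
| 2 | 0.992 | 1.086 | 0.913 |
| 3 | 0.995 | 1.149 | 0.866 |
| 5 | 1.026 | 1.370 | 0.749 |

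The averaged SD looks 4% to 25% low only against the pooled within-imputation SD, which is itself too large here. Against the complete-data SD it is about 1% low at most. A leaner model (baseline and earlier visits only) gives a shortfall of about 2-5%.

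**The case against.** The strongest objection is that the premise is not written down. The sentence on mean values covers listings only, and 'averaged' in a table title could equally mean that the 20 summary statistics are averaged. Under that reading the test level stays at about 4-5% and the SD is not too small. This stands as a limit: the error is conditional on per-patient averaging. It does not remove the point, because the SAP leaves both readings open and the only averaging it describes is per patient.

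The second objection is scale. The documents give no missing-data rate. Protocol 7.1 encourages patients who stop treatment to attend the remaining visits, and the Week 12 analysis window runs from day 71 to day 91, so missingness may be low. With 1 missing per arm the effect is barely visible. The p-values sit in descriptive tables; superiority rests on the between-arm contrast. All of this stands and keeps the point minor.

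A reader might go further and infer three things that the documents do not support:
- That the tables report SDs that are materially too small. Step 4 shows otherwise for the SAP's imputation model at 16 to 17 per arm.
- That false positives also arise for Skindex-29. Section 3.2.2 limits the t-tests to WI-NRS and WP-NRS, so Table 14.2.2.12 carries none.
- That the primary result is affected. The between-arm analyses on imputed data are pooled by Rubin's rule and do not use averaged values.

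**Conclusion.** The point holds in a narrow form and is minor. If 'averaged' means one mean per patient, the within-arm t-tests in Tables 14.2.1.2 and 14.2.2.2 do not hold their 5% level. At 16 to 17 per arm the level is about 5-6% with 1 missing, 6-7% with 2, 7-10% with 3 and 10-12% with 5. With complete data there is no effect.

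The figures rest on assumed missingness, completely random dropout, normal data and assumed correlations. The direction does not depend on the exact values: the hand check, which needs no correlation, gives nearly the same levels. The harm is confined to descriptive within-arm p-values, which could be over-read in a small trial with no multiplicity adjustment.

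**What to change.** Preferred: drop Tables 14.2.1.2 and 14.2.2.2. The observed-case summaries (14.2.1.1 and 14.2.2.1) already describe the data, and the pooled analyses (14.2.1.6 and 14.2.2.6) already carry the inference from imputed data. Table 14.2.2.12 can go for consistency, or stay with a definition of 'averaged'.

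If the tables are kept:
- State in the SAP what 'averaged' means.
- Show the number of patients actually observed at each visit.
- Remove the t-tests from these tables and confine them to the observed-case tables. Pooling them by Rubin's rule is also acceptable, though conservative here (1-4%).
- Do not replace the SD with the pooled within-imputation SD, which was 1.04 to 1.37 times the complete-data SD with 1 to 5 of 17 missing.

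The cost is an edit to the table shells and one or two sentences in SAP sections 3.2.2 and 5.5. No new data are needed and no planned between-arm analysis changes.
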